3. STUDY OBJECTIVES

The primary efficacy objective is to determine whether administration of FCX-007 in addition to standard of care improves wound healing as compared to standard of care alone (control) in children, adolescents, and adults with RDEB and confirmed mutation of the COL7A1 gene.

4. STUDY DESIGN

4.1 Overall Study Design

DEFI-RDEB is a multi-center, intra-subject randomized and controlled, open-label, Phase 3 study of FCX-007 for the treatment of RDEB wounds. FCX-007 is comprised of autologous fibroblasts isolated from the RDEB subject's skin biopsies and transduced with a virus containing the full-length COL7A1 gene to produce functioning type VII collagen.

The Screening Period consists of eligibility criteria evaluations, the collection of one set of three 3-4 mm biopsies for FCX-007 manufacturing, and the identification of potential target wounds with a minimum 12-week Wound Monitoring Period (through photography). The subject's potential target wounds will be imaged at the Screening visit by the Investigator or designee, if possible, and subjects will capture wound images via the photography vendor's mobile device-based imaging system at home weekly during this period. The wound characteristics observed during the monitoring period will be utilized to reduce bias in the pairing of target wounds for

treatment and efficacy and safety evaluation. The Screening Period is expected to have a duration of approximately 4-6 months, to accommodate subject scheduling and variations in manufacturing duration.

Prior to randomization, target wounds will be identified that meet selection criteria based on review of the photographic images from the Wound Monitoring Period. Up to three target wound pairs, each wound between approximately 5 cm² and 50 cm² for subjects 2 to 6 years of age and wounds between approximately 10 cm² and 50 cm² for subjects 7 years of age and older, will be identified for each subject. The Investigator will assign a First (Primary) Pair for primary endpoint evaluation, additional applicable pairs will be designated as Second (Secondary) and Third (Tertiary) Pairs. The First Pair will be the wounds that have been open for the longest duration of time (recorded in weeks, to the closest week) within the Wound Monitoring Period immediately prior to Day 1 (Visit 2), have shown the least variation of wound area over the Wound Monitoring Period and are similar in anatomical location and size. The target wounds in the Second Pair and in the Third Pair will be assigned with similar hierarchical criteria. Following pairing, target wounds will be randomly assigned as the treatment wound (FCX-007 is administered) or control wound.

Subjects will receive intradermal injections of FCX-007 in each specified treatment wound in two or more treatment sessions. Intradermal injections of FCX-007 0.25 mL per linear cm are administered around, and within 1 cm of, the perimeter and across each applicable wound bed; a maximum of 15 mL (in 60 injections) may be administered per session, and the Investigator is encouraged to administer the full quantity of FCX-007 should the total wound size permit. As the wound size and shape will dictate the quantity of FCX-007 to be administered, it is not possible to calculate this until after randomization. As a general rule, the maximum number of injections of FCX-007 is expected to be used over a surface area of approximately 60- 80 cm².

[figure not shown]
The first treatment session occurs at Day 1 (Visit 2) and the second at Week 12/Month 3 (Visit 3). At these visits, the treatment wound in the First Pair will be injected first, followed sequentially by the Second and Third Pairs (if applicable, and only as sufficient product is available). It is permissible for a treatment wound in the Second or Third Pair to be partially treated due to insufficient quantity of product, if the treatment wound in the First or Second Pair was completely treated.

At selected sites only, in a subset of subjects that consent to additional research skin biopsy collection, an additional single treated wound (not from a target wound pair) may be injected with FCX-007 at Day 1 (Visit 2) and Week 12/Month 3 (Visit 3) only.

Additional treatment sessions may occur at Week 24/Month 6 (Visit 4) and Week 36/Month 9 (Visit 5) when unclosed treatment wounds may be re-treated, and unclosed control wounds may be treated.

Safety and efficacy assessments will occur at scheduled intervals through Week 48/Month 12 (Visit 6), when the treatment period is completed, and a long-term safety follow-up period (through 15 years) commences for subjects who have received one or more FCX-007 injections of any volume.

The study schema is presented below.

4.1.1 Schedule of Visits and Assessments

Refer to Table 3 within the Protocol for the Schedule of Events.

4.1.2 Method of Randomization

This study will not have a separate control group. Randomization of target wounds in each target wound pair to either FCX-007 treatment (treatment wound) or untreated control (control wound) will be independently assigned on Day 1 (Visit 2) following target wound labeling and pairing into target wound pair(s).

Prior to the end of Wound Monitoring Period for the first subject, randomization codes for each subject's target wound pairs (First, Second, and Third Wound Pairs) assigning each target wound within the target wound pair(s) to either FCX-007 treatment (treatment wound) or untreated control (control wound) will be generated by the study biostatistician. The full randomization list will be retained by Abond. The randomization codes will be provided to the investigative site in sealed envelopes. The randomization envelope for a subject, available only to limited site personnel, will not be opened until the First, Second, and Third Wound Pairs are selected for that subject (refer to Protocol Section 8.3.1.2 for additional details).

4.1.3 Blinding

Screening and Baseline wound assessments (WAs) necessary for identification, mapping, selection, and labeling are to be performed by the PI, or trained, medically qualified Sub-Investigator (Sub-I), who will remain unblinded to wound treatment assignment throughout the study.

The Investigator Assessment of Complete Wound Closure of Target Wounds must be performed by a Blinded Investigator at Weeks 12, 22, and 24 (Table 3 of protocol). Blinded assessment is also preferred at Weeks 36 and 48. This assessment is to be completed after removal of subject's dressings from target wound pairs (treatment and control wounds) and prior to any potential disruption of the target wounds (i.e., surgical pen markings, target wound tracing, bacterial culture of wounds if applicable, FCX-007 administration preparation or administration, or collection of biopsies).

The Blinded Investigator will not have access to the subject's source documents, CRFs, or electronic data capture (EDC) as information regarding target wound randomization and treatment information is available. The Blinded Investigator's assessments will be maintained as separate source documents and stored in a separate location. Written or verbal communication about treatment assignment or interval changes in wounds between those involved in administering FCX-007 (including study team members, subjects and those accompanying subjects at any visit, or others who have knowledge of the wound treatment assignment) and the Blinded Investigator will be discouraged, and a verbal reminder of this requirement will be stated by the Blinded Investigator at the time of the assessments.

5. EFFICACY AND SAFETY ENDPOINTS

5.1 Efficacy Endpoints

5.1.1 Primary Efficacy Endpoints

The primary efficacy endpoint is:

- Complete wound closure of the First Wound Pair at Week 24

5.1.2 Secondary Efficacy Endpoints

The secondary efficacy endpoints are as follows:

- Complete wound closure of the First Wound Pair at Week 12
- Complete wound closure of all wounds at Week 24
- Complete wound closure of all wounds at Week 12

5.1.3 Supportive Efficacy Endpoints

The supportive efficacy endpoints are as follows:

- Durability of wound closure from Week 24 through Week 48
- Durability of wound closure from Week 24 through Week 36
- Durability of wound closure from Week 12 through Week 48
- Durability of wound closure from Week 12 through Week 36
- Change from baseline in surface area of each wound at Weeks 12, 24, 36, and 48
- Change from baseline in Wong-Baker FACES Pain Rating Scale at Weeks 12, 24, 36, and 48
- COL7 expression in a treated wound as assessed by immunoelectron microscopy (IEM) and immunofluorescence (IF) at Weeks 36 and 48

5.2 Safety Endpoints

Safety evaluations include AEs, vital signs, physical and skin examinations, clinical laboratory testing, RCL testing, antibody response to COL7, neoplasms (such as SCC or sarcoma) and/or inflammation.

6. STATISTICAL AND ANALYTICAL PLANS

6.1 General Methodology

All statistical processing will be performed using SAS® unless otherwise stated. No interim analyses are planned. The primary analysis will occur once all subjects have completed Week 24. No statistical testing will be performed.

Descriptive statistics will be used to provide an overview of the efficacy and safety results. For categorical parameters, the number and percentage of subjects in each category will be presented. For continuous parameters, descriptive statistics will include n (number of subjects), mean, standard deviation (SD), median, minimum and maximum.

The primary method of handling missing efficacy data will last observation carried forward (LOCF).

Efficacy analysis will be performed on the Full Analysis Set (FAS) population.

The number of subjects in each analysis set will be summarized. Reasons for study withdrawal during the treatment period will be summarized using frequencies and percentages.

Reported AEs, medical history terms and prior and concomitant procedures and therapies will be classified on the basis of Medical Dictionary for Regulatory Activities (MedDRA) terminology. Prior and concomitant medications will be classified on the basis of World Health Organization Drug Dictionary (WHO-DDE) terminology.

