10.7. HANDLING OF MISSING DATA

Every effort will be made to collect complete data at all visits.

The SAP will detail methods for missing values. The primary method of handling data will be last observation carried forward (LOCF).

Standard clinical monitoring and data management practices will be used to ensure the integrity of data.

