6.1.5 Handling of Dropouts or Missing Data

If a partial date is reported where the day is missing, then the day will be imputed as the first day of the month unless the month is the same month as the first injection then the day will be that of first injection with the month and year remaining the same. If a partial date is reported where the month is missing, then the month will be imputed to January unless the year is the same year as the first injection then the month will be that of first injection with the year remaining the same. If a partial date where both the day and month is missing, follow details as stated previously.

Missing adverse event dates will be imputed using partial date imputation rules as previously described in this Section. Missing data for other parameters will not be imputed for analysis unless otherwise defined.

The primary method for handling missing data for the analysis of the primary and secondary endpoints will be LOCF.

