6.7.3 Supportive Efficacy Analysis

Durability of wound closure from Week 24 through Week 48 is defined as a wound assessed as closed at Week 24 (with confirmatory closure at Week 22), as well as closed at the Week 36 and Week 48 WA. Summaries will be done for both First wounds and all qualifying wounds (those assessed as closed at Week 24) by treatment group.

Durability of wound closure from Week 24 through Week 36 is defined as a wound assessed as closed at Week 24 (with confirmatory closure from Week 22), as well as closed at the Week 36 WA. Summaries will be done for both First wounds and all qualifying wounds (those assessed as closed at Week 24) by treatment group.

Durability of wound closure from Week 12 through Week 48 is defined as a wound assessed as closed at Week 12, as well as closed at Weeks 24 (with confirmatory closure at Week 22), 36 and 48 WAs. Summaries will be done for both First wounds and all qualifying wounds (those assessed as closed at Week 12) by treatment group.

Durability of wound closure from Week 12 through Week 36 is defined as a wound assessed as closed at Week 12, as well as closed at Weeks 24 (with confirmatory closure at Week 22) and 36 WAs. Summaries will be done for both First wounds and all qualifying wounds (those assessed as closed at Week 12) by treatment group.

The Wong-Baker FACES Pain Rating Scale will be summarized by visit with changes from Baseline at Weeks 12, 24, 36 and 48. Summaries will be done for the First wound pair, and all wound pairs, as well as by maximum across wounds (treated and control).

COL7 expression in treated wounds as assessed by IEM and IF at Weeks 36 and 48 will be presented in listings.

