6.7.5 Sensitivity Analyses

Sensitivity analyses will be included in order to assess the impact of missing data.

In the event of missing Week 24 WAs (with confirmatory closure at Week 22) for either wound, sensitivity analyses will consider these wounds as failures.

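### SAP 6.1 and 6.1.5 give LOCF different scopes; under 6.1, a wound confirmed closed at Week 24 and then never seen again counts as durably closed

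*SAP*

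**What the plan says.** **LOCF, general rule.** SAP 6.1: "The primary method of handling missing efficacy data will last observation carried forward (LOCF". No endpoint is excepted.

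**LOCF, dedicated section.** SAP 6.1.5: "The primary method for handling missing data for the analysis of the primary and secondary endpoints will be LOCF". For the rest: "Missing data for other parameters will not be imputed for analysis unless otherwise defined".

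**Protocol.** Section 10.7 says "The primary method of handling data will be last observation carried forward (LOCF", but it also leaves the details of missing-value handling to the SAP. Protocol 10.4 makes the SAP operative where the two differ.

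**Status of durability.** All four durability endpoints appear in SAP 5.1.3 under "The supportive efficacy endpoints are as follows". They are efficacy endpoints, but neither primary nor secondary.

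**Definition.** SAP 6.7.3 defines durability from Week 24 through Week 48 as a wound "closed at Week 24 (with confirmatory closure at Week 22), as well as closed at the Week 36 and Week 48 WA". It is summarised for First wounds and for "all qualifying wounds (those assessed as closed at Week 24) by treatment group". The other three endpoints are built the same way. None has a rule for a missing assessment.

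**Sensitivity analysis.** SAP 6.7.5 addresses a missing Week 24 assessment with its Week 22 confirmation: "sensitivity analyses will consider these wounds as failures". It does not mention Week 36 or Week 48.

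**The concern.** Durability asks whether a closed wound stays closed. Every wound that enters the question starts closed. Carrying that starting state into an unobserved Week 36 or Week 48 therefore supplies the answer the endpoint is meant to test.

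The assumption is not harmless in this disease. The SAP introduction reports that most recurrent wounds heal within 3 weeks and reopen within 3 weeks, and recurrent wounds are eligible. Carrying a Week 24 closure to Week 48 spans 24 weeks. If closures occur roughly as the sample-size section assumed (60% of treated wounds, 10% of control wounds), most wounds exposed to this rule would be treated wounds.

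Two programmers could also each follow the SAP and handle the same unobserved wound differently. With no testing planned, the reported counts and percentages are the evidence, so their definition matters.

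**Working it through.** **The plan's own figures.** The documents give no figure for durability or for LOCF. The one calculated figure is the original power. An exact two-sided McNemar test with 24 pairs, 60% versus 10% closure and 70% discordance gives 0.8512, which agrees with the stated 85%. Nothing below depends on it.

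**Step 1: which rule reaches durability.**

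| | Primary and secondary | Durability (supportive) |
|---|---|---|
| SAP 6.1 | LOCF | LOCF |
| SAP 6.1.5 | LOCF | not imputed unless otherwise defined |

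The sections agree in the first column and conflict in the second.

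**Step 2: follow one wound** that is closed at Weeks 22 and 24 and missing at Weeks 36 and 48.

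- Under 6.1, closed is carried to both visits and the 6.7.3 definition is met: durable.
- Under 6.1.5, there is no value at either visit. The definition is not met as observed. Whether the wound then counts as not durable or leaves the denominator is not stated.
- A wound seen closed at Week 36 and missing at Week 48 is also durable through Week 48 under 6.1.
- For the endpoints that start at Week 12, a closed state is likewise carried into later missing readings.
- A wound open at Week 24 does not qualify, and LOCF would carry it forward as open.

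Until an open reading is observed, LOCF can fill a qualifying wound only with closed. It can call a reopened wound durable, but it cannot call a durable wound reopened. The error therefore runs one way.

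**Step 3: when a reading is truly missing.** SAP 6.1.3 maps early-termination and unscheduled readings to Week 36 (Days 211 to 294) or Week 48 (Days 295 to 379). Step 2 applies only if no such reading exists. The same section drops assessments after Day 379, so a late Week 48 reading would also count as missing.

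**Step 4: size.** SAP 7 gives 6 enrolled subjects, hence at most 6 First treatment wounds. Let k be the wounds closed at Weeks 22 and 24, m those of them with no later reading, and D the denominator. Assume every observed wound stays closed.

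- LOCF: k/D
- Missing as not durable: (k − m)/D
- Observed cases: (k − m)/(D − m)
- First minus second: m/D, which per wound is 1/6 = 16.7 points with D = 6, or 1/4 = 25 points with D = 4

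| k | m | D | LOCF | Missing as not durable | Observed cases |
|---|---|---|---|---|---|
| 4 | 1 | 6 | 4/6 = 66.7% | 3/6 = 50.0% | 3/5 = 60.0% |
| 4 | 2 | 6 | 4/6 = 66.7% | 2/6 = 33.3% | 2/4 = 50.0% |
| 6 | 1 | 6 | 6/6 = 100% | 5/6 = 83.3% | 5/5 = 100% |
| 4 | 2 | 4 | 4/4 = 100% | 2/4 = 50.0% | 2/2 = 100% |

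The values of k and m are illustrative, because the documents give no missing-data pattern. Both denominators are shown because 6.7.3 does not say plainly whether the First-wound summary keeps wounds that were open at Week 24.

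**The case against.** The strongest reply is that 6.1 is an overview and 6.1.5 is the section on missing data, so the specific rule governs and durability is not imputed. SAP 6.7.3 also defines durability by assessments, and a wound that was not assessed does not meet those words. This reading is plausible and may be the intended one. The text does not settle it: the exception in 6.1.5 for anything otherwise defined can be read as pointing back to 6.1, and no order of precedence is given.

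There are also safeguards. Protocol 7.6.2 and 8.5.2.4 ask for every effort to complete the end-of-treatment assessments after discontinuation (7.6.2: within 12 weeks), and SAP 6.1.3 can map them to Week 36 or Week 48. All visits are listed and discontinuations are summarised, so with 6 subjects a missing reading can be traced. These measures narrow the gap without closing it.

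A reader might infer more than the documents support:

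- *That any wound with no reading after Week 24 becomes durable.* Only a wound already closed at the start of the window does.
- *That the protocol is a second, independent source of unlimited LOCF.* It defers to the SAP.
- *That 100% against 50% measures the conflict between the two sections.* The 50% comes from counting missing as not durable, which neither section states for Weeks 36 and 48. Observed cases give 2/2, the same percentage as LOCF on half as many observed wounds.

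**Conclusion.** The conflict in scope is real, and the SAP does not resolve it for durability. Under 6.1, a wound confirmed closed at Week 24 and then unobserved is reported as durable, and any resulting error is upward. The size is 16.7 points per such First treatment wound with all 6 in the denominator, or 25 points if 4 qualify, against missing counted as not durable. Against observed cases the percentage may not move at all, although the count of wounds actually seen to be durable does.

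It would go too far to say that the plan definitely counts unseen wounds as durable, or that a main result is at risk. The first depends on 6.1 prevailing over 6.1.5. On the second, the primary and secondary endpoints use LOCF under both sections, durability is supportive, and the SAP plans no testing. The point is worth correcting because it is cheap and the sample is small enough for one wound to show.

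**What to change.** **SAP 6.1.** Limit the LOCF sentence to the primary and secondary endpoints, to match 6.1.5.

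**SAP 6.7.3.** Add a rule along these lines: *LOCF is not used for durability. A wound counts as durable only if it was observed closed at every required assessment. The number of qualifying wounds with a missing Week 36 or Week 48 reading is shown by treatment group, with the observed-case proportion alongside.*

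The observed-case figure belongs there because the main rule is conservative: a wound that stayed closed but was not seen counts against durability. Showing both figures with the missing counts lets the reader see how much rests on unobserved wounds. The change to 6.1 also settles the pain scores, which are supportive efficacy data with the same ambiguity; they would then be left unimputed.

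**Cost.** A few sentences of SAP text and no new data. With 6 subjects, the reported durability percentage could fall noticeably if even one or two closed wounds lack a later reading.

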6.1.1 Statistical Analysis

All analyses will be performed by Abond CRO using SAS® Version 9.4 or later. All summary tables and data listings will be prepared utilizing SAS® software.

The standard operating procedures (SOPs) of Abond will be followed in the creation and quality control of all data displays and analyses.

6.1.2 Baseline Definition

Baseline is defined as the last non-missing assessment prior to first injection. For the primary endpoint, baseline refers to Day 1 (pre-initial injection) images, measurements and assessments.

6.1.3 Visit Windowing

Data will be summarized based on nominal visit indications with the exception of data captured at early termination and unscheduled visits; data from early termination and unscheduled visits will be summarized based on mapped visit values. The analysis windows for early termination and unscheduled visits are presented in the following table.

Analysis Windows for Early Termination and Unscheduled Visit Mapping

Scheduled Visit	Protocol Specified Window	Analysis Window
Week 12	Week 11 to 16 (Day 78 to 113)	Week 6 to 18 (Day 43 to 126)
Week 24	Week 23 to 28 (Day 162 to 197)	Week 18 to 30 (Day 127 to 210)
Week 36	Week 35 to 40 (Day 246 to 281)	Week 30 to 42 (Day 211 to 294)
Week 48	Week 47 to 52 (Day 330 to 365)	Week 42 to 54 (Day 295 to 379)

Early termination and unscheduled visits will not be mapped to the Week 22 visit.

Data collected at early termination and unscheduled visits prior to study day 78 will not be analyzed, with the exception of those identified as baseline values. Data from assessments performed after study day 379 will not be included in analyses.

The definition for the study day included in each study window is defined as below:

Study Day prior to Day 1 = Visit Date – Day 1 Date

Study Day on or after Day 1 = Visit Date – Day 1 Date + 1

If an assessment's mapped visit is a visit at which the subject has data from a scheduled visit present, or if no analyses are planned for the assessment at the mapped visit, the data collected at the early termination or unscheduled visit will be presented in listings only.

In the event of multiple values from unscheduled or early termination assessments within an analysis window, the value closest to the scheduled visit target study day will be used for analyses. If two values tie as closest to the time point (for example, one value is before and the other value is after the time point), then the later value will be selected.

Data collected at all visits will be included in the data listings with visit presented as reported by the site.

